17.1 Sample size calculation

The primary objective of this trial is to compare long-term glycaemic control of IDegLira vs. IGlar in insulin naïve subjects with T2DM inadequately controlled with OAD(s). This is established by comparing the time from randomization to the need for treatment intensification for IDegLira and IGlar using a stratified log-rank test.

Formally, let D be the hazard ratio for time to treatment intensification. The null-hypothesis of no treatment difference will be tested against the alternative hypothesis as given by

H₀: D = 1 against H_A: D ≠ 1

The need for treatment intensification is determined as the HbA_{1c} ≥ 7% at 2 consecutive visits from week 26 (including week 26, if HbA_{1c} was ≥ 7% at week 12). Subjects withdrawing from the trial or discontinuing treatment will contribute to the primary analysis as needing rescue therapy from the time of withdrawal/discontinuation. The data will inherently be interval censored, since HbA_{1c} is only measured at the scheduled visits while subjects may reach an HbA_{1c} ≥ 7.0% at any time between 2 visits.

The sample size is based on time from randomisation to the need of treatment intensification, a 1:1 randomisation scheme, a 5% significance level and exponential survival.

Based on experience from the phase 3a development program for IDegLira and IDeg, it is assumed that around 45% in the IDegLira arm will need treatment intensification compared with around 55% in the IGlar arm during the 2-year treatment period. Subjects withdrawing from the trial or discontinuing treatment are included in these proportions as needing treatment intensification. [Table 17-1](#) shows power calculations for varying effect sizes.

Table 17-1 Power for varying treatment differences

Percentage of subjects needing treatment intensification before end of trial	IDegLira: 40% IGlar: 55% HR: 0.65	IDegLira: 45% IGlar: 55% HR: 0.75	IDegLira: 50% IGlar: 55% HR: 0.86	IDegLira: 55% IGlar: 65% HR: 0.72
800 subjects	99%	83%	31%	85%
1000 subjects	>99%	90%	37%	92%

HR: hazard ratio

From these assumptions the sample size is set to 500 subjects per treatment arm; in total 1000 subjects will be randomised. This will provide 90% power to detect a hazard ratio of 0.75 for IDegLira relative to IGlar (i.e., a 25% reduction in the risk of needing treatment intensification) using a two group log-rank test and a two-sided significance level of $\alpha = 0.05$.

17.2 Definition of analysis sets

The following analysis sets are defined in accordance with the ICH-E9 guidance¹:

Full Analysis Set (FAS): includes all randomised subjects. In exceptional cases, subjects may be eliminated from the FAS. In such cases the elimination will be justified and documented.

The statistical evaluation of the FAS will follow the intention-to-treat principle and subjects will contribute to the evaluation “as randomised”.

Safety Analysis Set (SAS): includes all subjects receiving at least 1 dose of the investigational product or comparator. Subjects in the safety set will contribute to the evaluation “as treated”.

Randomised subjects who are lost to follow up and where no exposure information of the investigational product or comparators is available after randomisation will be handled as unexposed.

Before data are released for statistical analysis, a review of all data will take place to identify protocol deviations that could potentially affect the results. Any decision to exclude any subject or observation from the statistical analysis is the joint responsibility of the members of the study group. The subjects or observations to be excluded and the reason(s) for their exclusion will be

documented and signed by all parties. The documentation will be stored together with the remaining trial documentation.

17.3 Primary endpoint

The following endpoint will be assessed up to 104 weeks. Time from randomisation to inadequate glycaemic control and need for treatment intensification defined as an $\text{HbA}_{1c} \geq 7\%$ at 2 consecutive visits from week 26 (including week 26, if HbA_{1c} was \geq to 7% at week 12).

Subjects withdrawing from the trial or discontinuing treatment will contribute to the primary analysis as needing rescue therapy from the time of withdrawal/discontinuation. The data will inherently be interval censored, since HbA_{1c} is only measured at the scheduled visits while subjects may reach an $\text{HbA}_{1c} \geq 7.0\%$ at any time between 2 visits (including week 26 if HbA_{1c} was $>$ to 7% at week 12).

The primary endpoint will be analysed using a stratified log-rank test where treatment, baseline HbA_{1c} group and previous OAD treatment will be included as strata in the model.

The variable “baseline HbA_{1c} group” is a dichotomised baseline HbA_{1c} variable with 2 categories: $\text{HbA}_{1c} < 8.5\%$ or $\text{HbA}_{1c} \geq 8.5\%$.

The variable “previous OAD treatment” is a categorical variable with 2 categories: OAD(s) + sulphonylurea or OAD(s).

Formally, let D be the hazard ratio for time to treatment intensification. The null-hypothesis of no treatment difference will be tested against the alternative hypothesis as given by

$H_0: D = 1$ against $H_A: D \neq 1$

Kaplan-Meier curves by treatment arm and strata from the model will be presented.

Sensitivity analysis

The following two sensitivity analysis will be carried out.

The first sensitivity analysis will take the interval censored nature of the data into account by using a semi-parametric proportional hazards regression model for interval censored data. The chosen model can be viewed as an extension of Turnbull’s method²⁴ from a non-parametric model to a semi-parametric proportional hazards models as described in Alioum.²⁵

The log-likelihood function of the data under the proportional hazards assumption can be expressed as:

$\sum_{i=1, \dots, n} \log \left(\sum_{j=1, \dots, m} \mu_{ij} (S(p_{j-1})^{\exp(\beta zi)} - S(p_j)^{\exp(\beta zi)}) \right),$
where:

- μ_{ij} is 1 if subject i's observed interval encompass the j^{th} Turnbull interval and 0 if this is not the case
- p_j is the right endpoint of the j^{th} Turnbull interval
- z_i is the covariate vector for subject i and β is the corresponding vector of regression coefficients
- S is the survivor function for individuals with covariate vector $z_i = 0$, based on the Turnbull method, i.e. a survivor function whose positive mass is restricted to the Turnbull intervals but which otherwise is free of constrictions (non-parametric)

Baseline HbA_{1c} group and previous OAD treatment will be included in the model by stratification, i.e. when expressing the model with regards to the integrated hazard using the identity - $\log(S(t)^{\exp(\beta z)}) = \Lambda(t, z)$, we have $\Lambda(t, z) = \Lambda_f(t) \exp(\beta z)$, where Λ_f is the integrated baseline hazard for baseline HbA_{1c} and previous OAD treatment stratum f, f = (HbA_{1c} < 8.5% and OAD(s), HbA_{1c} < 8.5% and OAD(s) + sulphonylurea, HbA_{1c} ≥ 8.5% and OAD(s), HbA_{1c} ≥ 8.5% and OAD(s) + sulphonylurea), while treatment and region will be included as factors in the model.

The test of no difference between treatment groups will be performed using a likelihood ratio test.

In the second sensitivity analysis the time to inadequate glycaemic control and need for treatment intensification will be compared between the IDegLira arm and the IGlar arm using a two-sided nonparametric test at a 5% significance level. The test will be a generalised log rank test for interval censored failure time data.²⁶ The analysis will not be based on any model assumptions such as proportional hazards. The possible failure times will be considered as a discrete set of time points corresponding to the scheduled visits. An alternative but technically equivalent model would be to view the failure time as a continuous variable which can only be observed to lie in the interval between the visit when treatment failure is established and the previous scheduled visit.

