4.2.2 Secondary endpoints

4.2.2.1 Supportive secondary endpoints

Supportive secondary efficacy endpoints

- Time from randomisation to $\text{HbA}_{1c} > 6.5\%$ at 2 consecutive visits from week 26* (including week 26, if HbA_{1c} was $> 6.5\%$ at week 12)
- Change from baseline in HbA_{1c} after 26 weeks of treatment*
- Change from baseline in body weight after 26* and 104 weeks of treatment
- Insulin dose after 26* and 104 weeks of treatment
- Responder after 26 and 104 weeks of treatment (yes/no):
 - $\text{HbA}_{1c} < 7.0\%*$
 - $\text{HbA}_{1c} < 7.0\%$ without weight gain
 - $\text{HbA}_{1c} < 7.0\%$ without treatment-emergent severe or blood glucose (BG) confirmed symptomatic hypoglycaemic episodes during the last 12 weeks of treatment
 - $\text{HbA}_{1c} < 7.0\%$ without treatment-emergent severe or BG confirmed symptomatic hypoglycaemic episodes during the last 12 weeks of treatment and without weight gain
 - $\text{HbA}_{1c} \leq 6.5\%*$
 - $\text{HbA}_{1c} \leq 6.5\%$ without weight gain
 - $\text{HbA}_{1c} \leq 6.5\%$ without treatment-emergent severe or BG confirmed symptomatic hypoglycaemic episodes during the last 12 weeks of treatment
 - $\text{HbA}_{1c} \leq 6.5\%$ without treatment-emergent severe or BG confirmed symptomatic hypoglycaemic episodes during the last 12 weeks of treatment and without weight gain

- Change from baseline after 26 weeks of treatment in:
 - Fasting plasma glucose (FPG)*
 - 9-point Self-measured plasma glucose (SMPG) profile:
 - 9-point profile (individual points in the profile)*
 - Mean of the 9-point profile
 - Prandial plasma glucose increments (from before meal to 90 min after breakfast, lunch and dinner). The mean increment over all meals will be derived as the mean of all available meal increments
- Change from baseline after 104 weeks of treatment in:
 - FPG
 - 9-point SMPG profile:
 - 9-point profile (individual points in the profile)
 - Mean of the 9-point profile
 - Prandial plasma glucose increments (from before meal to 90 min after breakfast, lunch and dinner). The mean increment over all meals will be derived as the mean of all available meal increments
- Change from baseline after 26 and 104 weeks of treatment in:
 - Blood pressure (systolic and diastolic)
 - Fasting C-peptide and fasting human insulin

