17.4 Secondary endpoints

17.4.1 Supportive secondary endpoints

17.4.1.1 Efficacy endpoints

Time from randomisation to HbA_{1c} > 6.5% at 2 consecutive visits from week 26.

Time from randomisation to HbA_{1c} > 6.5% at 2 consecutive visits from week 26 (including week 26 if HbA_{1c} was ≥ 6.5% at week 12).will be analysed and presented in the same way as the primary endpoint.

HbA_{1c}

Change from baseline in HbA_{1c} after 26 weeks of treatment will be analysed using the standard MMRM model.

Body weight

Change from baseline in body weight after 26 and 104 weeks of treatment will be analysed using the standard MMRM model.

Insulin dose after 26 and 104 weeks of treatment

The actual insulin dose will be summarised descriptively according to regimen as dose in units, and units/kg. The actual daily insulin dose will be analysed using the standard MMRM model.

HbA_{1c} responder after 26 and 104 weeks of treatment (yes/no)

Two dichotomous endpoints (responder/non-responder) will be defined based on whether a subject has met a specific target level after 26 and 104 weeks of treatment:

- HbA_{1c} target < 7.0%⁷
- HbA_{1c} target ≤ 6.5%²⁷

Analysis of each of the four responder endpoints will be based on a logistic regression model with treatment, HbA_{1c} group, previous OAD treatment and region as fixed factors and baseline HbA_{1c} value as a covariate. Subjects withdrawing from the trial or discontinuing treatment will be imputed as being non-responder from time of withdrawal/discontinuation in line with the evaluation of the primary endpoint.

HbA_{1c} responder endpoints without weight gain

Responder for HbA_{1c} without weight gain after 26 and 104 weeks of treatment will be defined as HbA_{1c} < 7.0% or ≤ 6.5% and change in body weight from baseline ≤ 0. Analysis of each of the 2 responder endpoints will be based on a logistic regression model with treatment, HbA_{1c} group, previous OAD treatment and region as fixed factors and baseline HbA_{1c} and baseline body weight as covariates. Subjects withdrawing from the trial or discontinuing treatment will be imputed as being non-responder from time of withdrawal/discontinuation in line with the evaluation of the primary endpoint.

HbA_{1c} responder endpoints without treatment-emergent severe or BG confirmed symptomatic hypoglycaemic episodes

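### Section 17.3 makes treatment a stratum of the primary log-rank test, and the time-to-HbA1c-above-6.5% endpoint has two different week-12 rules

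*Protocol*

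**What the plan says.** **Primary test.** Section 17.3 specifies a "stratified log-rank test where treatment, baseline HbA_{1c} group and previous OAD treatment will be included as strata in the model". Each of the two baseline variables has two categories (HbA1c below 8.5% or at least 8.5%; OADs with or without sulphonylurea). The same section sets the null hypothesis as a hazard ratio D of 1 between treatments.

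Two other places describe the test differently. Section 17.1 has a stratified log-rank test comparing IDegLira with IGlar, and computes power "using a two group log-rank test and a two-sided significance level". For the first sensitivity analysis, 17.3 says "Baseline HbA_{1c} group and previous OAD treatment will be included in the model by stratification". It lists the four resulting strata and enters treatment as a factor.

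**Time to HbA1c above 6.5%.** Both sections require values above 6.5% at two consecutive visits from week 26, with a rule for when week 26 itself may count. In 4.2.2.1 it counts if the week-12 HbA1c "was $> 6.5\%$ at week 12". In 17.4.1.1 it counts if the week-12 HbA1c "was ≥ 6.5% at week 12". Section 17.4.1.1 adds that this endpoint "will be analysed and presented in the same way as the primary endpoint". The responder endpoint in 17.4.1.1 is defined by "HbA_{1c} target ≤ 6.5"%, so exactly 6.5% is on target.

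**Clerical.** In the second paragraph of 17.3, the 7% week-12 qualifier reads "was $>$ to 7% at week 12", where the endpoint definition uses at-or-above.

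None of the four amendments changes section 17.

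**The concern.** A stratified log-rank test compares groups within strata. If the variable to be compared also defines the strata, nothing is left to compare. The sentence that fixes the confirmatory test therefore cannot test the hypothesis stated in the same section, and it disagrees with 17.1 and with the sensitivity model. The 6.5% endpoint inherits the problem because it is analysed like the primary endpoint.

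The two week-12 rules give one endpoint two event definitions. Under the 17.4.1.1 version, a subject at exactly 6.5% at week 12 and above 6.5% at week 26 fails on a single value above the threshold, although the endpoint asks for two. The endpoint is starred in 4.2.2.1 for public disclosure. In an open-label trial, choosing between the two rules after data have accrued invites questions about post hoc choice.

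**Working it through.** **1. The plan's own power figure.** Inputs from 17.1: 500 subjects per arm, 45% and 55% with events over 104 weeks, exponential survival, two-sided alpha 0.05.

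- Events = 500 × (0.45 + 0.55) = 500.
- HR = ln(1 − 0.45) / ln(1 − 0.55) = ln 0.55 / ln 0.45 = 0.7487, stated as 0.75.
- Schoenfeld: power = Φ(√500 / 2 × |ln 0.7487| − 1.96) = Φ(3.236 − 1.960) = Φ(1.276) = 89.9%.

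The stated 90% is reproduced for a comparison of two arms.

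**2. Treatment as a stratum.** At each event time in a stratum, the score adds d₁ − d·n₁/n and the variance adds d·(n₁/n)(1 − n₁/n)(n − d)/(n − 1). Here n and d are the numbers at risk and with an event, and the subscript 1 marks the IDegLira arm. With treatment, HbA1c group and OAD group as strata there are 2 × 2 × 2 = 8 strata, each holding one arm, so n₁/n is 0 or 1.

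- If n₁/n = 1, then d₁ = d and the score term is 0. If n₁/n = 0, then d₁ = 0 and the score term is 0.
- The variance term is 0 in both cases.

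The statistic is 0/0. Two simulated trials of 1000 subjects under the planning assumptions confirm it:

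| Simulated trial | Treatment among the strata | Four HbA1c × OAD strata |
|---|---|---|
| A | U = 0, V = 0 | U = −33.7, V = 127.3 |
| B | U = 0, V = 0 | U = −27.0, V = 122.3 |

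Over 1000 simulated trials, power was 89.3% with four strata and 89.5% unstratified. The simulation error is about 1 point: √(0.893 × 0.107 / 1000) = 0.0098. Stratum shares were assumed (40% with HbA1c at least 8.5%, 45% on sulphonylurea).

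**3. The two week-12 rules.** Take a subject with exactly 6.5% at week 12 and 6.8% at week 26.

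| Rule | Week-12 condition | Event at week 26? |
|---|---|---|
| 4.2.2.1 | above 6.5%: not met | No; needs week 38 also above 6.5%, or a later event |
| 17.4.1.1 | at or above 6.5%: met | Yes |

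The discontinuation rule in 6.4 does not hide the difference, since it needs at least 7% and the week-12 value is 6.5%.

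**4. How many subjects.** The protocol gives no week-12 HbA1c distribution, so this is wholly assumption-driven. Thirty scenarios were run: week-12 mean 6.3–7.1%, SD 0.6–1.0, within-subject correlation 0.6 or 0.8, drift 0.15% per year, values held to 0.1%.

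| Quantity | Share of all subjects | Per 1000 |
|---|---|---|
| Exactly 6.5% at week 12 | 3.3–6.6% | 33–66 |
| Also above 6.5% at week 26 (rules differ) | 1.8–3.5% | 18–35 |
| Of these, an event at week 38 under 4.2.2.1 | 1.1–2.5% | 11–25 |
| Of these, never an event under 4.2.2.1 | 0.2–0.4% | 2–4 |

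The share could be zero. The laboratory text (8.1.5, moved to 8.5 by Amendment 4) says database results are in SI units. Section 5.1 equates 7.0–11.0% with 53–97 mmol/mol, so one percentage point is (97 − 53) / (11.0 − 7.0) = 11 mmol/mol, and 6.5% is 53 − 0.5 × 11 = 47.5 mmol/mol. If values were held in whole mmol/mol, none would fall exactly on 6.5% unless converted and rounded. The protocol does not state the precision.

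**5. The 7% symbol in 17.3.** A subject at exactly 7.0% at week 12 and at least 7% at week 26 must stop trial product under 6.4, and discontinuation counts as an event in the primary analysis. The slip has essentially no effect on primary events.

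**The case against.** The strongest reply is that no competent analyst would be misled on the primary test. Section 17.3 states a null of no treatment difference and promises Kaplan-Meier curves by arm and by strata, naming the two separately. Section 17.1 says which arms are compared, and the sensitivity model lists the four strata. The literal test cannot be computed, so it could not produce a wrong result unnoticed. All of this stands: the intent is recoverable and no choice of method is in dispute. It does not make the sentence correct.

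On the 6.5% endpoint, the reply is that this is one symbol in a supportive endpoint, affecting only subjects at exactly 6.5%. A further simulation tested the effect on the treatment comparison: 12 scenarios of 200 trials, 500 per arm, with an assumed arm difference of 0.3 points in mean HbA1c and no dropout. The choice of rule moved the approximate hazard ratio by less than 0.006 on average and by at most 0.036 in any one trial. Those inputs are assumed too, but they give no sign of a material effect on the comparison, and none is claimed here. What remains is that two sections define one disclosed endpoint differently.

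Two smaller objections are fair. The four-stratum power simulation specifies stratum shares but no prognostic effect, so it says little about power when strata are prognostic; the 89.9% does not depend on it. The 7% symbol sits in a sentence explaining interval censoring, and a bar lost in PDF reading cannot be excluded, so it carries no weight.

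**Conclusion.** Both main points hold as errors of text. The sentence specifying the confirmatory test gives 0/0 if followed literally and contradicts 17.1 and the sensitivity model. The intended test is clear, and the sample size and the 90% power stand.

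For the 6.5% endpoint, 4.2.2.1 and 17.4.1.1 disagree for subjects at exactly 6.5% at week 12. The strict version is the coherent one: it keeps the requirement of two values above the threshold and agrees with the responder target. The number affected is unknown. Under the assumed distributions, 1.8–3.5% of subjects have a different event time or status and 0.2–0.4% a different final status; depending on how values are stored, it may be none. These should be corrected, but neither threatens the primary result.

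**What to change.** - **17.3, test specification:** a two-sided log-rank test comparing IDegLira with IGlar, stratified by baseline HbA1c group and previous OAD treatment (four strata). The 6.5% endpoint then inherits the correct test.
- **17.4.1.1, time to HbA1c above 6.5%:** change the week-12 condition from at-or-above 6.5% to above 6.5%, as in 4.2.2.1.
- **17.3, second paragraph:** while editing, align the 7% week-12 symbol with the at-or-above of the endpoint definition.

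The cost is text corrections in two sections. Sample size, power, visits and data collection do not change.

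### The proportional hazards sensitivity model uses baseline HbA1c only as a split at 8.5%; adding the continuous value within strata would recover a little power

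*Protocol*

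**What the plan says.** Protocol section 17.3 makes a stratified log-rank test the primary analysis. One stratification variable is the baseline HbA1c group, which "is a dichotomised baseline HbA_{1c} variable with 2 categories", cut at 8.5%. The other is previous OAD treatment, with or without sulphonylurea.

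The first sensitivity analysis in 17.3 is a semi-parametric proportional hazards model for interval-censored data. The same two variables define four strata, each with its own baseline hazard, "while treatment and region will be included as factors in the model". Treatment is tested by a likelihood ratio test. Baseline HbA1c does not appear as a continuous term.

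Section 17.4.1.1 analyses time to HbA1c above 6.5% as the primary endpoint is analysed. In the same section the responder logistic models carry the HbA1c group together with "region as fixed factors and baseline HbA_{1c} value as a covariate". The standard MMRM in section 17, used for change in HbA1c, likewise has the HbA1c group as a factor and the endpoint's own baseline value as a covariate.

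Section 11 describes 1:1 randomisation and names no stratification factor. None of the amendments shown changes section 17.

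**The concern.** Both time-to-event endpoints are defined by HbA1c staying at or above a threshold, so baseline HbA1c is a natural prognostic factor. Section 6.2 admits values from 7.0% to 11.0%. The upper group alone spans 2.5 percentage points. At an assumed hazard ratio of 1.5 per 1% HbA1c, hazards at its two ends differ by 1.5^2.5 = 2.8-fold, yet the model treats those subjects as alike.

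Elsewhere the sponsor pairs the group with the continuous value when the outcome is HbA1c. The two time-to-event endpoints depart from that without a stated reason, and no stratified randomisation requires the split to stand alone. At stake is a slightly attenuated hazard ratio and a slightly weaker test in one supporting model.

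**Working it through.** **1. The plan's own figure.** Section 17.1 assumes "a 1:1 randomisation scheme, a 5% significance level and exponential survival"; "it is assumed that around 45% in the IDegLira arm will need treatment intensification compared with around 55% in the IGlar arm"; and 500 subjects per arm.

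- Hazard ratio = ln(0.55)/ln(0.45) = 0.749.
- Events = 500 × 0.45 + 500 × 0.55 = 500.
- Power (Schoenfeld) = Φ(√500 × |ln 0.749|/2 − 1.96) = 89.9%. The Freedman form gives 89.5%, and the exponential-variance form 89.6%.

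The stated 90% is reproduced. It is computed "using a two group log-rank test and a two-sided significance level of" 0.05, so it does not depend on any regression covariate.

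**2. Why the standard error should not move.** With 1:1 allocation the standard error of the log hazard ratio is about 2/√events = 2/√500 = 0.089. It is governed by the number of events. A prognostic covariate acts instead by moving the estimate away from zero.

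**3. Continuous-time simulation.** There were 2000 trials of 1000 subjects per setting, with event rates held at 55% and 45%. A Cox model stratified by HbA1c group and OAD class was compared with the same model plus continuous HbA1c. The following inputs are assumptions that the protocol does not give:

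- Baseline HbA1c truncated normal on 7–11%, with mean about 8.5, SD 0.83 and 46% at 8.5% or above.
- Half the subjects on sulphonylurea.
- The prognostic strength shown in the first column.

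Region was not modelled.

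| Assumed HR per 1% HbA1c | Log HR, strata only | Log HR, plus continuous | SE, both | Power, strata only | Power, plus continuous | Squared z ratio |
|---|---|---|---|---|---|---|
| 1.0 | −0.293 | −0.293 | 0.090 | 89.4% | 89.5% | 1.00 |
| 1.25 | −0.296 | −0.297 | 0.090 | 90.1% | 90.3% | 1.01 |
| 1.5 | −0.301 | −0.306 | 0.090 | 91.3% | 92.4% | 1.03 |
| 2.0 | −0.316 | −0.331 | 0.090 | 94.6% | 96.3% | 1.09 |

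In the last row the hazard ratio moves from exp(−0.316) = 0.729 to exp(−0.331) = 0.718.

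**4. Visit-grid simulation, closer to the planned model.** There were 700 trials per setting, with a grouped-time complementary log-log model and stratum-by-visit intercepts.

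| Assumed log-hazard per 1% (HR) | Power, strata only | Power, plus continuous | Squared z ratio |
|---|---|---|---|
| 0.3 (1.35) | 90.0% | 90.6% | 1.01 |
| 0.5 (1.65) | 91.4% | 92.9% | 1.05 |
| 0.8 (2.2) | 94.6% | 96.1% | 1.13 |

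A second visit-grid run gave squared z ratios of 1.00, 1.01, 1.04 and 1.12 for log-hazards of 0, 0.3, 0.5 and 0.8. Power rose by 0 to about 1.5 points, and the standard error again stayed at 0.090.

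**5. Why the gain is small.** Under the step 3 distribution the SD of HbA1c within groups is 0.47, against 0.83 overall. The variance left within groups is (0.47/0.83)² = 32%. The 8.5% split already captures about two thirds of the covariate's variance.

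**The case against.** The strongest reply is that nothing here is false or contradictory, and that a logistic model and a stratified hazards model may properly carry different terms. Several parts of that reply stand.

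- **Precision.** A reader might infer that the split wastes precision. It does not: the standard error is unchanged. The gain in the test statistic comes from a hazard ratio conditional on more information.
- **Strata.** A reader might infer that the dichotomised strata bring no benefit. They do. They allow each stratum its own baseline hazard, need no linearity, and match the primary test. That argues for keeping them, not for omitting a slope within them. Region is already in this model and not in the primary test, so exact alignment was not the aim.
- **The main result.** A reader might infer that the primary test loses power, because the 8.5% definition stands under the primary endpoint. The remedy concerns a sensitivity analysis whose stated purpose is interval censoring.
- **Bias.** Within-stratum differences in baseline HbA1c between randomised arms are chance differences.
- **The reported hazard ratio.** A reader might take this model as the declared source of the trial's hazard ratio. It is the only hazard-ratio regression that the protocol describes for this endpoint. However, 17.3 specifies only its likelihood ratio test and does not say where a reported hazard ratio will come from.
- **Size.** The prognostic strength is assumed. Withdrawals and discontinuations count as events, and both arms are titrated to a fasting glucose target. Both could weaken the link with baseline, so the low end of the range is plausible. With 700 trials, the simulation error of one power figure near 90% is √(0.9 × 0.1/700) = 1.1 points.

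The narrow point survives. The protocol itself fixes the covariate list, the continuous value is omitted without a reason, and including it lost nothing detectable when it had no effect.

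**Conclusion.** The point holds as a minor efficiency and consistency remark on one model, applied to two endpoints. If baseline HbA1c is prognostic within strata, the sensitivity model's hazard ratio is slightly shrunk towards 1. Its likelihood ratio test then gives up about 0 to 2 percentage points of power for assumed hazard ratios of 1.0 to 2.2 per 1% HbA1c. The standard error stays at about 0.090.

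This rests on an assumed baseline distribution and an assumed log-linear effect, neither of which the protocol supplies. The documents do not support any conclusion that the primary analysis is wrong, that the trial is underpowered, or that the treatment comparison is biased.

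**What to change.** Leave the primary stratified log-rank test and the four strata as they are. In the first sensitivity analysis in 17.3, list baseline HbA1c as a continuous covariate, with one slope common to the strata, beside treatment and region. State that this also applies to time to HbA1c above 6.5% in 17.4.1.1. If the sponsor prefers to omit the term, a sentence giving the reason would suffice.

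The cost is a few words in the protocol or SAP and no new data, since HbA1c is already measured at screening and randomisation. The downside is one coefficient assumed log-linear, and a hazard ratio that must be described as conditional on baseline HbA1c within strata.
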